8.6 Clinical Laboratory Abnormalities and Other Abnormal Assessments

Laboratory abnormalities are usually not recorded as AEs unless considered to be clinically significant by the site clinician. An abnormal laboratory result will be considered an AE if it induces clinical signs or symptoms, if the abnormality is of a degree that requires active management (e.g. discontinuation of the study drug, dose modification) or when the event is requiring treatment or other therapeutic intervention (e.g. iron supplements, blood transfusion, etc.).

The Investigator will evaluate the relationship of any significantly abnormal result to protocol treatment and clinical condition, if possible. All clinically significant abnormal laboratory results will be followed until they return to normal or become stabilized.

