3 DESIGN

This is an open label, randomized, controlled, multicenter Phase 2 study of favipiravir in hospitalized subjects with COVID-19. Subjects will be randomized within their study site and stratified by the severity of their disease to receive either favipiravir + standard of care (SOC) or SOC alone (See Section 9.5 for details).

SOC will be site-specific and based on what each site is currently using for COVID-19 patients.

The dose regimen will be 1800 mg favipiravir BID plus SOC or SOC alone on Day 1 followed by 1000 mg BID favipiravir (800 mg BID for subjects with Child-Pugh A liver impairment) plus SOC or SOC for the next 13 days.

The study will have 14 days of treatment and 46 days of follow-up.

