5.4 Individual Stopping Rule

In addition to the above, a. subject should be removed from favipiravir treatment if one of the following criteria is met:

- AST or ALT $> 8 \times ULN$
- ALT or AST > 3 × ULN AND total bilirubin > 2 × ULN
- AST or ALT $> 3 \times ULN$ AND patient has right upper quadrant pain or eosinophilia
- Uric acid > 20mg/dL

A subject whose treatment is terminated should remain in the study for appropriate follow up assessments.

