6 STUDY TREATMENT - FAVIPIRAVIR

6.1 Study Drug

Favipiravir will be provided in 200 mg tablet form to be stored at controlled room temperature (15°C to 30°C [59°F to 86°F]) and shielded from light.

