#### 4.5.3. Laboratory Data

Clinical laboratory values will be expressed in SI units.

All laboratory data will be provided in data listings.

Abnormal clinical laboratory values that are clinically significant will be graded according to the CTCAE version 5.0. A listing of all abnormal laboratory values will be provided.

Shift tables for hematology and chemistry parameters from baseline to worst value will be provided by treatment group and overall. All unscheduled visits, if any, will contribute to the last or worst value.

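### Protocol 8.6 ties laboratory AEs partly to action on study drug, which only the favipiravir arm has, so laboratory AE counts and selectively graded values are not ascertained alike in the two arms

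*Protocol*

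**What the plan says.** Protocol 8.6 starts from a default: "Laboratory abnormalities are usually not recorded as AEs unless considered to be clinically significant by the site clinician". It then gives further routes by which a result becomes an AE: it produces signs or symptoms; it counts "if the abnormality is of a degree that requires active management (e.g. discontinuation of the study drug, dose modification"; or it counts "when the event is requiring treatment or other therapeutic intervention". No route has a numeric or grade threshold.

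Protocol 5.4 sets limits on AST/ALT (alone, or combined with bilirubin, right upper quadrant pain or eosinophilia) and on uric acid. It says a "subject should be removed from favipiravir treatment if one of the following criteria is met". SAP 1.2.4 repeats this.

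The study drug is favipiravir (Protocol 6.1: "Favipiravir will be provided in 200 mg tablet form"). Under Protocol 3, subjects are randomized "to receive either favipiravir + standard of care (SOC) or SOC alone", open label and without placebo.

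For analysis, Protocol 9.7 calculates the difference between arms in the proportion of subjects in each TEAE category. It also plans laboratory changes over time, Low/Normal/High counts by treatment at each visit, and shift tables for parameters with severity grades. SAP 4.5.3 plans listings and by-arm shift tables from baseline to worst value, with unscheduled visits included, and states: "Abnormal clinical laboratory values that are clinically significant will be graded according to the CTCAE version 5.0".

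**The concern.** An AE comparison is fair when the same finding is recorded in the same way in both arms. Here one of the recording routes is illustrated only by what is done to a drug that one arm does not receive. The remaining routes are open to both arms, but one of them is the opinion of a clinician who knows the allocation. Protocol 8.4.2 also excludes clinical events of COVID-19 progression from being AEs, so an unblinded clinician may put an SOC subject's abnormal result down to the disease and record nothing.

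Safety against SOC is a secondary objective and a listed secondary endpoint. Protocol 2.3 names uric acid as the exception to otherwise similar AE profiles for favipiravir and placebo, and uric acid is one of the 5.4 triggers. At stake is whether an excess of laboratory AEs on favipiravir can be read as a drug effect or may come partly from the recording rule.

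**Working it through.** The plan states no figure on this point, so the check is textual, followed by an illustration on assumed values.

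**Step 1: follow one value through each arm.** Take the same chemistry result, beyond a 5.4 limit, on a day when favipiravir is being dosed.

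- *Clinician considers it significant (8.6):* open to both arms, unblinded, no threshold.
- *Signs or symptoms (8.6):* open to both arms.
- *Treatment or other intervention (8.6):* open to both arms.
- *Active management as exemplified (8.6):* on favipiravir, met when the subject is stopped under 5.4 or the dose is changed. On SOC alone, there is no study drug to stop or change.

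So a favipiravir subject who is stopped has an AE without reference to the first three routes. The SOC subject has one only if one of those three applies.

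**Step 2: follow the same value into the analyses.**

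- *TEAE proportions and their between-arm difference (Protocol 9.7; counts and percentages in SAP 4.5.2):* affected.
- *CTCAE grades (SAP 4.5.3):* affected, because only values considered clinically significant are graded.
- *Low/Normal/High counts (Protocol 9.7):* not affected.
- *Baseline-to-worst shift tables (SAP 4.5.3):* independent of AE status. The SAP does not say whether they use reference ranges or grades; if grades, they would carry over the selection of which values are graded.

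The underlying data are comparable: AST, ALT, bilirubin and urate (Protocol 8.4) follow one schedule for both arms (Protocol 13).

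**Step 3: what the size depends on.** Let r be the true proportion of subjects reaching a 5.4 limit, the same in both arms. Suppose every such favipiravir subject is stopped and so recorded, and a share q of such SOC subjects is recorded through the other routes. Then

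spurious difference = r − r × q = r × (1 − q).

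Neither r nor q is in the documents. The values below are assumptions, applied to the planned 25 per arm (Protocol 9.2):

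- r = 4%, q = 75%: 0.04 × 0.25 = 1 percentage point.
- r = 12%, q = 50%: 25 × 0.12 = 3 expected AEs against 1.5; 0.12 × 0.50 = 6 points.
- r = 20%, q = 25%: 0.20 × 0.75 = 15 points.
- any r, q = 100%: 0 points.

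If only a share p of favipiravir subjects at a limit is recorded, the expression becomes r × (p − q), which is smaller.

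**The case against.** Six points can be made against this.

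- *The wording is open.* The examples in 8.6 are illustrative, so active management could include stopping or adjusting another medicine in an SOC subject. That is a possible reading, but 8.6 names no such action, and a site applying it has only the study-drug examples to go on.
- *Extreme values would probably be recorded in either arm.* A result beyond the 5.4 limits may well be called significant whatever the allocation. This stands, and is why the bias may be zero.
- *The window is limited.* Favipiravir is planned for Days 1 to 14; afterwards neither arm has study drug to stop. This stands for the AE rule. The restriction on grading has no such limit.
- *A uric acid excess may be real.* Protocol 2.3 reports one against placebo in double-blind studies. This stands: the issue is that AE counts cannot show how much of an excess is real, not that any excess would be an artefact.
- *Other laboratory tables exist.* They do, and they confine the problem to AE counts and graded values. However, the Low/Normal/High counts appear in Protocol 9.7 and not in SAP 4.5.3, and SAP 5 does not list that as a change.
- *The trial is an exploratory study of about 50 subjects, and no test or decision rule uses laboratory AE counts.* This stands and limits the weight of the point.

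A reader might infer that every favipiravir value beyond a limit is an AE and no SOC value is. The documents do not support that: it looks at one route in 8.6 and ignores three that apply to both arms, and 5.4 says only that a subject should be removed.

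**Conclusion.** The concern holds in a limited form. The AE definition for laboratory results in Protocol 8.6 is not arm-neutral as exemplified, and SAP 4.5.3 leaves the choice of which values to grade to open-label opinion. Between-arm comparisons of laboratory AE counts and of graded values can therefore be biased towards an excess on favipiravir. The size cannot be derived from the documents. It is zero if every SOC value at a 5.4 limit is recorded, and 1 to 15 percentage points over the assumed ranges r = 4% to 20% and q = 25% to 75%, provided that every favipiravir subject at a limit is stopped and recorded.

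A reader might also infer that the trial cannot tell drug effect from disease on laboratory harms. That goes too far. The laboratory values are collected on the same schedule in both arms, and the by-arm shift tables and Low/Normal/High counts do not depend on AE status. The supported conclusion is narrower: AE counts alone cannot make that separation. The point makes no comment on whether the stopping limits are right.

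**What to change.** 1. In Protocol 8.6, add that any result meeting a laboratory limit listed in 5.4 is recorded as an AE in both arms, regardless of action on study drug. The stopping limits are unchanged.
2. In SAP 4.5.3, grade all values of CTCAE-gradable parameters by program in both arms and tabulate the worst post-baseline grade by arm. Use scheduled visits for the between-arm comparison, so that any difference in how often subjects are rechecked does not enter it. Keep the planned worst-value shift tables that include unscheduled visits.
3. State in the SAP that between-arm conclusions on laboratory safety rest on these tables and not on laboratory AE counts.

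The cost is a few more laboratory AE entries in the SOC arm, one sentence in the protocol and one extra programmed table. The data are already collected. Steps 2 and 3 change only the SAP and can be done even if the protocol is not amended.

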8.7 Handling of Overdose

An overdose is defined as any dose greater than the highest daily dose included in this document. Any overdose must be recorded. If the overdose is associated with an AE, that AE must be recorded, assessed for seriousness, and reported as an SAE.

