6.2 Standard Dose

Subjects randomized to the favipiravir + SOC arm will be administered loading doses of 1800 mg BID (Ideally 12 hours apart but 10–16 hours is allowed) on Day 1, and then maintenance dosing of 1000 mg twice daily BID (Ideally 12 hours apart but 10–16 hours is allowed) on Days 2–14 beginning 24 hours after the first dose. Day 1 is deemed to be the first 24 hours after enrollment into the study, with time 0 (time of first dose) occurring as soon as possible after the subject's eligibility has been confirmed.

An exception to the above maintenance dose will be made for those subjects entering the study with a Child-Pugh liver impairment of grade A who will receive favipiravir 800 mg BID on Days 2 through 14.

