6.6 Treatment Precautions

An overdose is defined as any dose of study drug given to a subject or taken by a subject that exceeds the dose described in this document. In the event of an overdose, the subject should be treated symptomatically, and the Sponsor informed.

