8.4.5 Definition of Serious Adverse Events

An SAE is an AE from this study that results in any of the following outcomes:

- Death (even if caused by COVID-19 all deaths are recorded as SAEs)
- Life-threatening situation (subject is at immediate risk of death)
- Inpatient hospitalization or prolongation of existing hospitalization
- Persistent or significant disability/incapacity
- Congenital anomaly/birth defect in the offspring of a subject who received study drug

NOTE: Important medical events that may not result in death, be immediately life-threatening, or require hospitalization, may be considered an SAE when, based upon appropriate medical judgment, they may jeopardize the subject *and* may require medical or surgical intervention to prevent one of the outcomes listed in this definition.

A life-threatening AE is defined as any adverse experience that places the subject in the view of the Investigator, at immediate risk of death from the event as it occurred. This does not include an event that might have led to death, if it had occurred with greater severity.

"Inpatient hospitalization" means the subject has been formally admitted to a hospital for medical reasons, for any length of time. Presentation and care within an emergency department does not necessarily constitute an SAE. Complications that occur during hospitalization are AEs. If a complication prolongs hospitalization, it is an SAE.

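### Protocol 6.6 and 8.7 set different overdose thresholds on Days 2 to 14, and 8.7 as worded makes any AE with an overdose an SAE, whatever its outcome

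*Protocol*

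**What the plan says.** The protocol defines overdose twice, and neither place refers to the other.

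- Section 6.6 (Treatment Precautions) takes as its threshold whatever dose the protocol describes: "An overdose is defined as any dose of study drug given to a subject or taken by a subject that exceeds the dose described". The consequences are symptomatic treatment and informing the Sponsor.
- Section 8.7 (Handling of Overdose): "An overdose is defined as any dose greater than the highest daily dose included in this document". The consequences are that the overdose is recorded and, if an AE accompanies it, "that AE must be recorded, assessed for seriousness, and reported as an SAE".

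Section 6.2 gives the doses. Favipiravir subjects "will be administered loading doses of 1800 mg BID" on Day 1, then "maintenance dosing of 1000 mg twice daily BID" on Days 2 to 14. The exception is Child-Pugh A subjects, "who will receive favipiravir 800 mg BID on Days 2 through 14". The synopsis and 6.3 also allow the dose to be altered after consultation with the Sponsor.

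On seriousness, 8.4.5 is outcome-based: "An SAE is an AE from this study that results in any of the following outcomes". Overdose is not on its list. Section 8.5 uses the 8.4.5 definition again as its test of seriousness for SUSARs. Section 8.4.6 tells a site reporting an SAE to mark the event as serious on the AE eCRF. Protocol 9.7 and SAP 4.5.2 then summarise serious TEAEs by treatment group, and 9.7 adds the difference in proportions.

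**The concern.** There are two separate defects.

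First, for 13 of the 14 treatment days the two definitions disagree about which intakes are overdoses. The errors in the gap are foreseeable: a loading dose continued by mistake, a home dose doubled, or a Child-Pugh A subject given the standard maintenance dose. Sites could classify the same event differently, depending on which section they had open.

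Second, the 8.7 reporting sentence asks for a seriousness assessment and then prescribes the result. Taken at its word, a mild AE with an overdose becomes an SAE. The same event may not be serious under 8.4.5, or for SUSAR purposes under 8.5. SOC-alone subjects receive no study drug, so this can add serious events to one arm only. Safety against SOC is a stated secondary objective.

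**Working it through.** The documents state no overdose ratio, so there is no figure to reproduce. The check is arithmetic on the protocol's own doses.

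**Inputs (protocol 6.2):** load 1800 mg BID; maintenance 1000 mg BID; Child-Pugh A maintenance 800 mg BID. Tablet strength is 200 mg (6.1).

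**Daily doses:** 2 × 1800 = 3600 mg; 2 × 1000 = 2000 mg; 2 × 800 = 1600 mg.

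**Width of the gap on Days 2 to 14:**
- Standard maintenance: 3600 / 2000 = 1.80; excess 1600 mg/day, or 1600 / 200 = 8 tablets.
- Child-Pugh A: 3600 / 1600 = 2.25; excess 2000 mg/day, or 2000 / 200 = 10 tablets.

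On Day 1 both sections give the same daily ceiling, 3600 mg.

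**Three dosing errors under each definition:**

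| Event on a maintenance day | Intake | Assigned | 6.6 | 8.7 |
|---|---|---|---|---|
| Loading dose continued | 3600 mg | 2000 mg | overdose | not an overdose |
| One home dose doubled | 2000 + 1000 = 3000 mg | 2000 mg | overdose | not an overdose |
| Child-Pugh A subject given 1000 mg BID | 2000 mg | 1600 mg | overdose | not an overdose |

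**Sensitivity to the wording of 8.7.** The ratios assume that 8.7 means the study regimen and compares daily totals. If it covers every regimen mentioned in the protocol, the first day of the Ebola regimen in 2.3 is 2 × 2400 + 1200 = 6000 mg, giving 6000 / 2000 = 3.0 and 6000 / 1600 = 3.75. If each single intake is set against 3600 mg, the multiples of a single maintenance dose are 3600 / 1000 = 3.6 and 3600 / 800 = 4.5. So 1.8 and 2.25 are the most conservative of these readings.

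**Effect of the SAE sentence.** The path is 8.7 (report as an SAE), then 8.4.6 (mark as serious on the eCRF), then 9.7 and SAP 4.5.2 (subjects with a serious TEAE, by arm). With about 25 subjects per arm, one additional subject moves the favipiravir percentage by 1 / 25 = 4 points. The tables count subjects, so this holds only for a subject with no other serious TEAE.

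**The case against.** A reader might infer that excess doses would go unrecorded. The documents do not support that. Site staff give all inpatient doses, and compliance is recorded dose by dose (6.5). Discharged subjects keep a diary card (6.3.1), tablets are counted at visits, and the accountability log goes to the Sponsor for checking (7.7). The SAP summarises total drug received and percent compliance, lists each administration (4.5.1) and lists all protocol violations (2.2). Section 6.6 still requires the Sponsor to be told. What may be lost is the overdose label and the handling that 8.7 attaches to it.

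A reader might also multiply 3600 mg by 14 days and treat the total as the exposure that could escape notice. That case is implausible. Staff would have to give the wrong inpatient dose for 13 days, and outpatients receive tablets only to the next visit plus one day.

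On the SAE sentence, the sponsor may have meant reporting only if the event is serious, since assessing seriousness otherwise serves no purpose. That is plausible, but the condition is not written. Nor can the sentence be passed off as reporting without classification, because 8.4.6 has the site mark the event as serious.

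It is also fair that the planned comparison is descriptive, that no overdose frequency is given, and that at the 8.7 threshold the SAE rule would seldom be triggered. The last point shows that the two defects interact: how often the SAE rule applies depends on which definition a site uses.

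**Conclusion.** Both contradictions stand as written. On Days 2 to 14, intake above the assigned 2000 mg/day (1600 mg/day for Child-Pugh A) and up to 3600 mg/day is an overdose under 6.6 and not under 8.7, a gap of up to 1.8 or 2.25 times the assigned dose. This rests on reading 6.6 as the dose described for that subject on that day; a reading that removes the conflict leaves 6.6 with no clear threshold. It also rests on reading 8.7 as the highest daily dose of the study regimen.

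Under its literal wording, the SAE sentence conflicts with 8.4.5 and 8.5 and can add non-serious AEs to the serious-TEAE summary of the favipiravir arm only, at about 4 points per affected subject with no other serious TEAE. That is a per-subject figure, not a forecast. It would go too far to conclude that the safety comparison will be materially distorted, because the documents give no frequency and plan no test. The primary endpoint is not affected. This is an internal inconsistency that should be corrected. Which overdose threshold is right is not judged here.

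**What to change.** 1. Reconcile 6.6 and 8.7 into one overdose definition, stated once and cross-referenced. The threshold is for the sponsor to set. The text should say whether it applies to a single dose or a daily total, and how it applies to Child-Pugh A subjects and to dose alterations agreed with the Sponsor.
2. Reconcile the reporting sentence in 8.7 with 8.4.5 and 8.5, so that only AEs meeting 8.4.5 are classified and tabulated as serious TEAEs. If the sponsor wants rapid notice of overdoses, collect it separately and keep it out of the SAE tables.
3. Put the same rule in the eCRF instructions.

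The cost is a few sentences of protocol text and one eCRF instruction. Depending on the threshold chosen, there may be a few more overdose records.

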9 STATISTICAL METHODS

9.1 General Considerations

This study is intended to support a Phase 3 registrational trial in this patient population by providing information on the treatment effect on an unambiguous indicator of antiviral activity, i.e., the time to viral clearance, as well as to estimate the treatment effect on a number of important clinical and symptomatic disease correlates. Proof of concept will be established by a significant treatment effect on the primary endpoint of time to viral clearance. Based upon available data, a two-arm study of approximately 50 total subjects will be sufficient to provide reasonable assurance that the endpoints chosen for a confirmatory trial will elucidate treatment differences between favipiravir + SOC and SOC. Statistical significance testing will be used to assess the relative strength of evidence of the primary and secondary endpoints; given that this trial is intended as a proof of concept, a two-sided alpha-level of 0.10 will be used for significance testing.

It is important to ensure that reasonable certainty is achieved in the conclusions reached for key secondary endpoints, therefore key secondary endpoints will be adjusted for multiple statistical testing through a gatekeeping hierarchical methodology, as follows: Statistical significance for the first secondary endpoint, according to the order outlined in the endpoints section of this protocol, will be declared only if the primary endpoint has previously reached statistical significance. Subsequent endpoint analyses in the order presented will be declared significant

only if the previous endpoint in order has reached statistical significance. All analyses of secondary endpoints will also be conducted at the two-sided alpha-level of 0.10. The order of secondary endpoint analysis will be the following: the study-specific 6-point ordinal scale; time to clinical recovery; reduction in disease symptoms; reduction in oxygen/ventilation requirements.

Tabulations will be produced for appropriate demographic, baseline, efficacy, pharmacokinetic, and safety parameters. For categorical variables, summary tabulations of the number and percentage of subjects within each category (with a category for missing data) of the parameter will be presented. For continuous variables, the number of subjects, mean, median, standard deviation (SD), minimum, and maximum values will be presented, as well as 2-sided 95% confidence intervals (CIs). Summaries of categorical data will include counts and percentages, along with 2-sided 95% CIs. Kaplan Meier methods will be used to summarize the time-to-event endpoints, including 25th, 50th (median), and 75th percentiles with associated 2-sided 95% CIs, as well as percentage of events and censored observations.

Complete details of all statistical analyses, including methods for handling missing data, will be included in a formal statistical analysis plan (SAP), to be completed as soon as possible after study initiation.

